### **8.5 Rescreening**

Note, for subjects who are rescreened, their Day 1 labs will be used as their Screening and Day 1 values.

### **8.6 Baseline Definition**

For all variables, baseline will be considered to be the last value obtained prior to the date and time of incision. Change from baseline will be the difference between the value at a given time point and the baseline value. The baseline value corresponds to the screening visit in the study schedule.

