### **8.7 Study Day, Visit Window, and COVID-19**

For each patient, the day of surgery will be considered Study Day 1. Each assessment will be assigned a study day. The calculation for study day is dependent on whether the actual date of assessment is before or after the date of study Day 1 and is calculated as follows:

Before study Day 1:

study day = (date of assessment – Date of first dose of study medication Day 1).

On or after study Day 1:

study day = (date of assessment – Date of first dose of study medication Day 1) +1.

Days within the screening period will be numbered with negative numbers until day -1 defined as the day before AML-488 treatment (Day 1).

If the full date of the assessment is not known or not imputable based on the guidelines in Section 7.3, then no study day will be assigned. Study Day, and any corresponding durations will appear partial or missing in the listings.

For each patient, the end of the study is defined as the date of their last contact in this study.

Data will be analyzed based on the categorized visit captured in the database. No dates will be used to reassign visits or define visit windows. Although Day 15 or Early Termination is defined with +/-8 days, extensions to the visit window may be allowed due to impacts related COVID-19. Although Day 28/End of Study is defined with +/- 5 days, extensions to the visit window may be allowed due to impacts related COVID-19.

Any impacts due to COVID-19 will be noted in the study documentation.

The visits captured in the database include:

- Screening (Day -28 to Day -1)
- Baseline (Day 1) (pre- and post-operative)
- Day 15 or Early Termination

QMS Document Name: Statistical Analysis Plan	Page 15 of 29
QMS No (include version ref): STF-015-GL.02	Document date: 09JUL2019
CONFIDENTIAL	

- Day 28/End of Study

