#### **14.2 Vital Signs**

The actual values and the change from baseline in vital signs will be summarized over time with n, mean, standard deviation, and median, minimum, and maximum.

Vital signs i.e. height, weight, systolic blood pressure, diastolic blood pressure, heart rate, and respiratory rate will be summarized descriptively over time by individual Cohorts (i.e., Cohorts: A, A1, A2, A3, A4, A5, A6, B, B1, B2).

Furthermore, the number and percentage of subjects based on reference ranges will be described according to the derived categories (i.e. Low, Normal, High) for vital signs.

A listing of vital signs will be presented for all measurements

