Data from unplanned determinations, i.e. usually determinations where the investigator felt follow-up (FU) was necessary, will be included in the number and frequency counts of clinically significant values. They will also be included in the data listings.

A listing of laboratory values will be presented for all measurements and for abnormal findings, i.e. measurements outside of reference ranges. Laboratory values that are outside of reference ranges will be flagged in the data listings, along with corresponding reference ranges.

Shift tables showing changes with respect to toxicity grade according to NCI-CTCAE version 5.0 will be listed using the worst grade.

Laboratory values will be listed by timepoint (screening, prior to ALM-488 infusion (baseline), after ALM-488 infusion, Day 15, Day 28), overall and by individual Cohorts (i.e., Cohorts: A, A1, A2, A3, A4, A5, A6, B, B1, B2) and for all patients.

Data from unplanned visits will not be summarized but will be included in the data listings.

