#### **14.5 Physical Examinations**

Results from physical examinations will be summarized by visit/timepoint (screening, prior to ALM-488 infusion (baseline), after ALM-488 infusion, Day 15, Day 28), change from baseline by individual Cohorts (i.e., Cohorts: A, A1, A2, A3, A4, A5, A6, B, B1, B2).

PE will be provided in a data listing by subject.

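### The SAP gives three incompatible baselines, and the one stated for all variables allows readings taken after the ALM-488 infusion to serve as baseline

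*SAP*

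**What the plan says.** SAP 8.6 opens with a rule for every variable: "baseline will be considered to be the last value obtained prior to the date and time of incision". The same short section closes with a different one: "The baseline value corresponds to the screening visit in the study schedule". SAP 8.7 places Screening at Day -28 to Day -1.

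Two later sections use a third timepoint. SAP 14.3 states: "Laboratory values will be listed by timepoint (screening, prior to ALM-488 infusion (baseline), after ALM-488 infusion, Day 15, Day 28". SAP 14.5 says physical examination results will be "summarized by visit/timepoint (screening, prior to ALM-488 infusion (baseline), after ALM-488 infusion, Day 15, Day 28), change from baseline by individual Cohorts". Both list screening as something other than baseline. SAP 14.2 plans change from baseline ("The actual values and the change from baseline in vital signs will be summarized over time") but gives no baseline of its own.

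Two further statements bear on the derivation. SAP 8.7 says "Data will be analyzed based on the categorized visit captured in the database", and one of the visits it lists is "Baseline (Day 1) (pre- and post-operative". For rescreened subjects, SAP 8.5 says "their Day 1 labs will be used as their Screening and Day 1 values", without saying which Day 1 sample is meant.

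On timing, SAP 4.1 has the drug given 3-5 hours (B1) or 1-3 hours (B2) before surgery. SAP 12 plots image intensity ratio against the time from injection to incision, by dose level, but the supplied text gives no length for that interval in Cohort A. SAP 14.1 starts the treatment-emergent period at the infusion.

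**The concern.** Baseline for a safety variable should be the state before exposure. Here the anchor for all variables is incision, which follows the infusion. A value obtained in between is post-drug, yet 8.6 would make it the reference for later values. An acute effect that persists would then show as no change, and one that has resolved would show as a false change in the opposite direction. The anchor also disagrees with the treatment-emergent rule in 14.1: the same reading could be recorded as a treatment-emergent event and used as the subject's baseline.

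Apart from bias, the rules do not agree on which record to use. Safety is the primary objective. The outputs that depend on baseline are change from baseline for vital signs, laboratory values and physical examinations, and the laboratory shift tables. Adverse event and DLT outputs, actual values, the Low/Normal/High categories, CTCAE grade by visit and the listings do not depend on it.

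**Working it through.** The plan states no figure on this point, so there is none to reproduce. The check compares the rules and then works out the error that follows.

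**1. Which record each rule selects**

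| Source | Record selected |
|---|---|
| SAP 8.6, first sentence | Last value before incision; may be before or after infusion |
| SAP 8.6, last sentence | Screening, Day -28 to Day -1 |
| SAP 14.3 and 14.5 | Value before infusion, distinct from screening |

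Where a subject has both a screening value and a Day 1 pre-infusion value, the screening rule differs from the other two even if nothing is measured between infusion and incision. The one exception is laboratory values of rescreened subjects, for whom 8.5 equates the two. The incision and pre-infusion rules differ only if a reading falls between infusion and incision.

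**2. Whether that interval exists.** By design it does in Cohort B: 1-3 or 3-5 hours between dosing and surgery. Those 12 subjects are 12/48 = 25.0% to 12/21 = 57.1% of the planned total. This is the share with a stated lead time, not the share affected.

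**3. Error per subject.** Let B be the pre-infusion value, E the acute effect present in the last pre-incision reading, and Y any later value.

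- Change under the incision rule: Y - (B + E)
- Change from the pre-infusion value: Y - B
- Difference: -E

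**4. One subject, heart rates assumed** (screening 72, pre-infusion 80, after infusion but before incision 90, Day 15 80). Change at Day 15:

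- Screening rule: 80 - 72 = +8
- Pre-infusion rule: 80 - 80 = 0
- Incision rule: 80 - 90 = -10

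Without the reading of 90, the incision rule also gives 0, but the screening rule still gives +8.

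**5. Cohort mean, six subjects in B1 or B2.** If k of the 6 have such a reading, the bias is -(k/6)E. With an assumed E of 10 bpm:

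| k | Bias in mean change (bpm) |
|---|---|
| 0 | 0 |
| 1 | -(1/6) × 10 = -1.7 |
| 3 | -(3/6) × 10 = -5.0 |
| 6 | -(6/6) × 10 = -10.0 |

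The bias is proportional to E.

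**6. Shift tables.** One subject reclassified in a six-subject cohort moves a cell by 1/6 = 16.7 percentage points.

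**The case against.** The strongest reply is that the bias is hypothetical. No supplied text schedules a vital sign or laboratory sample between infusion and incision. If the post-infusion readings are all post-operative, the incision and pre-infusion rules select the same value and the bias is zero. The only early post-infusion samples with stated times are the blood allergy samples in 14.6, which have no planned change from baseline and so support nothing here. All of this stands, and it is why the size is given as a range that includes zero.

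Second, the wording in 14.3 and 14.5 labels a timepoint and is not a formal definition. A reader could take it as the local answer for laboratory values and physical examinations, leaving vital signs as the clearest output governed by 8.6 alone. That is fair, but a local label does not cancel a rule stated for all variables, and it directly contradicts the screening sentence.

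Third, the Day 1 visit name may simply cover two timepoints, and a post-dose sample standing in for Screening under 8.5 is unlikely to be intended. Both are reasonable readings. These points are secondary: the visit label does not resolve the conflict, and 8.5 needs only a clarifying word.

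Finally, the affected outputs are descriptive summaries of small cohorts, and the optimal dose is chosen on DLTs and fluorescence. This limits the consequence but leaves the primary-objective tables without one reproducible baseline.

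**Conclusion.** The concern holds. SAP 8.6 contradicts itself, and its screening sentence also contradicts 14.3 and 14.5. This follows from the text and rests on no assumption about the assessment schedule. The incision anchor admits post-infusion values, and nothing in 8.6 excludes them.

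The bias is conditional on two things: a reading between infusion and incision, and that reading differing from the pre-infusion value. Where both hold, the error is -E per affected subject and -(k/6)E in a six-subject cohort mean. E, k and the heart rates are assumptions. The protocol's assessment schedule, which was not among the text available for this review, would settle whether k can exceed zero. The SAP should be corrected before the safety tables are programmed.

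**What to change.** Replace the text of SAP 8.6 with: *For all safety variables, baseline is the last non-missing value obtained before the start of the ALM-488 infusion (Day 1 pre-infusion; screening if no Day 1 pre-infusion value exists). All values after the start of infusion are post-baseline.* This removes both the incision anchor and the screening-visit sentence. The SAP text available plans change from baseline only for safety variables, so no planned change-from-baseline output loses its rule.

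Then:

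- In 8.7, separate the Day 1 visit into a pre-infusion timepoint and later Day 1 timepoints for analysis.
- In 8.5, state that only pre-infusion Day 1 laboratory values may stand in for Screening.
- In 14.2, 14.3 and 14.5, refer to 8.6 and do not restate a baseline.

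The cost is wording in these sections and one derivation rule, with no new assessments. The derivation needs either timepoint codes or clock times for Day 1 assessments. The current rule already presumes times that can be compared with incision, and SAP 9.1 already lists infusion start date and time. The data manager should confirm that the database holds them.

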### **8.7 Study Day, Visit Window, and COVID-19**

For each patient, the day of surgery will be considered Study Day 1. Each assessment will be assigned a study day. The calculation for study day is dependent on whether the actual date of assessment is before or after the date of study Day 1 and is calculated as follows:

Before study Day 1:

study day = (date of assessment – Date of first dose of study medication Day 1).

On or after study Day 1:

study day = (date of assessment – Date of first dose of study medication Day 1) +1.

Days within the screening period will be numbered with negative numbers until day -1 defined as the day before AML-488 treatment (Day 1).

If the full date of the assessment is not known or not imputable based on the guidelines in Section 7.3, then no study day will be assigned. Study Day, and any corresponding durations will appear partial or missing in the listings.

For each patient, the end of the study is defined as the date of their last contact in this study.

Data will be analyzed based on the categorized visit captured in the database. No dates will be used to reassign visits or define visit windows. Although Day 15 or Early Termination is defined with +/-8 days, extensions to the visit window may be allowed due to impacts related COVID-19. Although Day 28/End of Study is defined with +/- 5 days, extensions to the visit window may be allowed due to impacts related COVID-19.

Any impacts due to COVID-19 will be noted in the study documentation.

The visits captured in the database include:

- Screening (Day -28 to Day -1)
- Baseline (Day 1) (pre- and post-operative)
- Day 15 or Early Termination

QMS Document Name: Statistical Analysis Plan	Page 15 of 29
QMS No (include version ref): STF-015-GL.02	Document date: 09JUL2019
CONFIDENTIAL	

- Day 28/End of Study

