#### **14.3 Clinical Laboratory evaluations**

##### **Hematology, Clinical Chemistry, and Coagulation, Urinalysis**

All laboratory data will be listed by individual cohort, patient and time point and if normal ranges are available abnormalities will be flagged. Summary statistics will be provided by study dose and time point.

The Hematology parameters include: red blood cells, hemoglobin, hematocrit, mean corpuscular volume, mean corpuscular hemoglobin, mean corpuscular hemoglobin concentration, white blood cells, neutrophils, eosinophils, basophils, lymphocytes, monocytes, %neutrophils, %eosinophils, %basophils, %lymphocytes, %monocytes.

The clinical chemistry parameters include: alkaline phosphatase, AST/SGOT, ALT/SGPT, total bilirubin, calcium, phosphorus, blood urea nitrogen, creatinine, GFR, total protein, albumin, glucose, potassium, sodium, chloride, magnesium, bicarbonate, uric acid, lactate dehydrogenase.

Coagulation parameters include: PT, aPTT, INR.

The urinalysis analysis will include protein, blood, leukocytes, glucose, ketones and pH.

QMS Document Name: Statistical Analysis Plan	Page 22 of 29
QMS No (include version ref): STF-015-GL.02	Document date: 09JUL2019
CONFIDENTIAL	

Quantitative data will be examined for trends using descriptive statistics (number of patients with data, number of patients with missing values, mean, standard deviation, median, minimum, and maximum) of actual values and changes from baseline to each visit/time point. This will be presented by individual Cohorts (i.e., Cohorts: A, A1, A2, A3, A4, A5, A6, B, B1, B2).

Quantitative data based on reference ranges will be described according to the NCI-CTCAE version 5.0 grade at each visit over time and by individual Cohorts (i.e., Cohorts: A, A1, A2, A3, A4, A5, A6, B, B1, B2).

Qualitative data will be described according to the categories (i.e. Normal; Abnormal, Not clinically significant; Abnormal, Clinically significant; Missing) and by individual Cohorts (i.e., Cohorts: A, A1, A2, A3, A4, A5, A6, B, B1, B2).

Shift tables of quantitative data showing changes with respect to the normal range and clinical significance between baseline and endpoint post-baseline visits as well as the worst value at any post-baseline visit.

Shift tables of qualitative data showing changes between baseline and post-baseline visits.

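### SAP 8.7 pools early-termination records with Day 15 and bars the use of dates, so a record from outside Days 7-23 can enter the descriptive Day 15 safety summaries

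*SAP*

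**What the plan says.** SAP 8.7 lists the visits held in the database. One of them is "Day 15 or Early Termination", so a scheduled Day 15 assessment and a termination assessment share a label. The assignment rule is "Data will be analyzed based on the categorized visit captured in the database", followed by "No dates will be used to reassign visits or define visit windows". The same paragraph gives the visit a nominal window: "Although Day 15 or Early Termination is defined with +/-8 days, extensions to the visit window may be allowed due to impacts related COVID-19". The next visit is treated likewise ("Although Day 28/End of Study is defined with +/- 5 days"), with the same allowance for extension. SAP 8.7 also derives a study day for each assessment, unless its date is unknown and cannot be imputed.

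Several outputs are built on the visit label. SAP 14.3 asks for descriptive statistics "of actual values and changes from baseline to each visit/time point" and for CTCAE grades at each visit. It plans quantitative shift tables "between baseline and endpoint post-baseline visits as well as the worst value at any post-baseline visit", and then "Shift tables of qualitative data showing changes between baseline and post-baseline visits". SAP 14.5 summarises physical examinations at named time points that include Day 15 and Day 28 but no early-termination time point. The only data that SAP 14.3 keeps out of its summaries as a class are those from unplanned visits. SAP 8.4 summarises observed data only.

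**The concern.** A subject who leaves the study may be assessed soon after surgery or well after Day 15. Under SAP 8.7 that assessment carries the same label as a true Day 15 visit, and the plan forbids using its date to move it. A reader of a column headed Day 15 would take its values as describing patients about two weeks after infusion, and some might not.

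Safety is the primary objective, and SAP 14.3 and 14.5 name only two follow-up time points after the surgical period, Day 15 and Day 28. Cohorts have 3 to 6 subjects, so one misplaced value can shift a cohort mean visibly. The plan is also uneven: a laboratory value from an unplanned visit a few days after surgery is kept out of the by-visit summaries, whereas a termination value from the same day enters as Day 15.

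**Working it through.** **Step 1: the plan's own figures.** SAP 4.1 gives at least 3 cohorts, up to 6 dose cohorts in the design (SAP 4), 3-6 subjects per dose level, and 2 timing cohorts of 6.
- Escalation/de-escalation: 3 × 3 = 9 to 6 × 6 = 36.
- Timing: 2 × 6 = 12.
- Total: 9 + 12 = 21 to 36 + 12 = 48.

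These match the plan, and nothing below changes them.

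**Step 2: nominal windows (SAP 8.7).**
- Day 15 or early termination: 15 − 8 = 7 to 15 + 8 = 23.
- Day 28: 28 − 5 = 23 to 28 + 5 = 33.

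Within Days 1-33, a termination record from Days 1-6 or Days 24-33 lies outside the nominal Day 15 window. Under the label rule it would still be analysed as Day 15.

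**Step 3: which outputs depend on the label.**

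| Output | SAP section | Depends on the Day 15 label? |
|---|---|---|
| Laboratory values and changes by visit | 14.3 | Yes |
| CTCAE grade by visit | 14.3 | Yes |
| Qualitative laboratory shifts | 14.3 | Yes |
| Physical examination by time point | 14.5 | Yes |
| Quantitative shifts to the endpoint visit | 14.3 | Unclear: if endpoint means the last visit, a termination value belongs there |
| Worst post-baseline value or grade | 14.3 | No |
| Adverse event tables | 14.1 | No |
| DLT Evaluable Set | 5 | No: it has its own criterion of Day 15 ± 8 |

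**Step 4: weight of one record.** If every subject in the cohort has a value, one record has weight 1/n. A value that differs by D from the mean of the others moves the cohort mean by D/n.
- n = 3: 1/3 = 33.3%, a shift of 0.33D.
- n = 6: 1/6 = 16.7%, a shift of 0.17D.
- n = 12 (Cohort B overall): 1/12 = 8.3%, a shift of 0.08D.

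**Step 5: how often.** The documents give no early-termination rate. The rates d below, 2% to 20%, are assumptions. The chance of at least one early termination in a cohort is 1 − (1 − d)^n. For example, with d = 5% and n = 3 it is 1 − 0.95³ = 14.3%.

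| Assumed rate d | n = 3 | n = 6 | Expected among 48 (48 × d) |
|---|---|---|---|
| 2% | 5.9% | 11.4% | 1.0 |
| 5% | 14.3% | 26.5% | 2.4 |
| 10% | 27.1% | 46.9% | 4.8 |
| 20% | 48.8% | 73.8% | 9.6 |

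These are upper limits for the problem at each rate. Some terminations will fall within Days 7-23 and be correctly shown, and some will leave no assessment at all.

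**The case against.** The strongest reply is that analysis by nominal visit is a deliberate and common choice, and that a reader can recover the timing. Study day is derived, all laboratory values are listed by subject and time point, and trial end dates and reasons for discontinuation are listed (SAP 9.2). No test, DLT decision or stated dose-selection criterion uses a Day 15 laboratory mean. Table specifications sit in a separate document (SAP 2.1), which may flag or footnote termination records. All of this stands, and it keeps the point minor. It does not remove the point, because the summary column as specified still carries a label that some of its values may not fit.

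Four stronger readings are tempting, and the documents do not support them.
- *Values from any day belong to the Day 15 visit.* The visit has a nominal window of Days 7-23. The gap is that the analysis does not enforce it.
- *COVID-19 delays are unlimited.* The SAP states no cap, but it allows extensions only for COVID-19 impacts, which are to be noted in the study documentation. This is an intended accommodation.
- *Subjects who stop early are the most likely to have abnormal values.* Nothing in the documents shows this. The reasons in SAP 9.2 include adverse event and death, but also loss to follow-up, technical problems and withdrawal by the subject.
- *All shift tables are distorted.* The worst-value and worst-grade shifts are independent of the label.

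The weights 1/3 and 1/6 also need care. They apply to any subject's value in a cohort of that size. The error depends on D, which is unknown.

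**Conclusion.** The point holds in limited form. Followed exactly, SAP 8.7 places an early-termination record from outside Days 7-23 in the Day 15 column of the descriptive laboratory and physical-examination summaries, the by-visit CTCAE grades and the qualitative shift tables. This follows from a stated rule and is not simply missing detail. Its effect on a cohort mean is D/3 to D/6 per record for cohorts of 3 to 6, assuming complete data. Its frequency rests on an assumed early-termination rate and is probably low. The primary safety conclusions drawn from adverse events, DLTs and worst post-baseline values are not at risk. The change is worth making because it is cheap, but nothing in the trial depends on it.

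**What to change.** Amend SAP 8.7 as follows.
1. Use the study day already derived. Count an early-termination record as Day 15 only if it falls in Days 7-23. Otherwise show it in a separate early-termination row of the by-visit tables.
2. If a subject has both a Day 15 record and a termination record, use the Day 15 record for the Day 15 summary.
3. Put a termination record that has no study day in the early-termination row.
4. Keep Day 15 visits delayed by COVID-19 under Day 15, with a footnote giving the actual study day.
5. Keep every record in the worst-post-baseline summaries and in the listings.

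Because the two kinds of record share a label, the rule should also say how a termination record is recognised. The discontinuation data listed under SAP 9.2 could serve if the database holds no separate flag.

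The cost is slightly fewer values in the Day 15 column, one extra row in the by-visit tables and the programming for it. No value is discarded, and no sample size, test or trial conduct changes.
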